**Table 7. Summary of treatment-emergent adverse events in cohort 2**

Category	DM-101 (N=4) f n (%)	Placebo (N=1) f n (%)	Total (N=5) f n (%)
Any TEAE	56 4 (100.0)	2 1 (100.0)	58 5 (100.0)
IMP-related TEAEs	50 4 (100.0)	0 0 (0.0)	50 4 (80.0)
Severe TEAEs	0 0 (0.0)	0 0 (0.0)	0 0 (0.0)
Serious TEAEs	0 0 (0.0)	0 0 (0.0)	0 0 (0.0)
TEAE leading to discontinuation*	2 2 (50.0)	0 0 (0.0)	2 2 (40.0)

Abbreviations: TEAE = Treatment-emergent adverse event; n = the number of subjects with at least one TEAE; f = the number of TEAEs

\*One of the discontinued subjects had 2 reasons for discontinuation, both withdrawal of consent and 2 Grade 3 local injection site reactions after 2 injections of IMP.

Based on the findings of the interim analysis and in order to ensure the safety of the study subjects, the dose and dose escalation scheme for further cohorts were decided to be revised.

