### **VISIT 2**

Subjects allocated into cohorts 3 and 4 (Table 8) will enter Turku University Hospital's Emergency Care unit, and after a brief medical review and other eligibility assessments they will receive a single s.c. injection of 30 ng of DM-101 or placebo. The subjects will remain confined in the hospital for approximately 6 h following dosing.

Dosing will be staggered in such a way that 2 sentinel subjects, 1 receiving DM-101 and 1 receiving placebo, will be dosed first in a double-blind fashion. Dosing of the remaining subjects in the cohort will be initiated no sooner than 22 h after the sentinel subjects have completed their Visit 2 dosing, without safety findings that would meet the study's stopping or treatment discontinuation criteria (see Section 9). Subjects in the main treatment group in each cohort will also receive treatment in a staggered way, with 2 subjects starting first to receive doses and the remaining subjects starting to receive doses no sooner than approximately 22 h after the first two subjects of the main group have received their Visit 2 dosing.

Visit 2 of cohort 4 subjects will take place after Visit 2 of cohort 3 has been completed.

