### **VISITS 3-6**

After Visit 2, dosing in each cohort will be allowed only if the study's stopping and treatment discontinuation criteria have not been met on the previous dosing visit (see Section 9).

All subjects will return to the hospital for another 4 visits (Visit 3, Visit 4, Visit 5 and Visit 6) on a biweekly basis for the subsequent dosings. In cohort 3, subjects will receive a single s.c. injection on each of these visits. In cohort 4, subjects will receive a single s.c. injection on Visits 3 and 4 and a series of 2 or 3 s.c. injections on Visits 5 and 6, respectively, with a minimum of 30 min interval between subsequent injections. Each injection will be given at a slightly different site of the exterior surface of the upper arm. The injections will alternate between the right and left arm.

Dose escalation to the 200 ng daily dose (Visit 5) in cohort 4 will only take place after a favourable recommendation from the SRC, once it has reviewed all available safety data so far collected in the study, including data from Visit 5 of cohort 3.

On each of the Visits 3-6, dosing will be staggered in the same way as on Visit 2, i.e. 2 sentinel subjects, 1 receiving DM-101 and 1 receiving placebo, will be dosed first in a double-blind fashion. Dosing of the remaining subjects in the cohort will be initiated no sooner than 22 h after the sentinel subjects have completed their dosing, without safety findings that would meet the study's stopping or treatment discontinuation criteria (see Section 9). Subjects in the main treatment group in each cohort will also receive treatment in a staggered way, with 2 subjects starting first to receive doses and the remaining subjects starting to receive doses no sooner than approximately 22 h after the first two subjects of the main group have received their dosing.

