### **Visit 2**

During the first treatment visit (Visit 2), a single dose of 30 ng of DM-101 or corresponding placebo s.c. injection will be administered as described in Section 3.2. Table 12 (see Section 6.5) shows the procedures that will take place, before and after dosing. Dosing will be initiated only if the results of the pre-dosing brief medical review and other eligibility

assessments are satisfactory. The subjects will remain confined in Turku University Hospital's Emergency Care Unit for approximately 6 h following their dosing.

Treatment will be staggered in such a way that 2 sentinel subjects, 1 receiving DM-101 and 1 receiving placebo, will be dosed first in a double-blind fashion. Dosing of the remaining subjects in the cohort will be initiated no sooner than 22 h after the sentinel subjects have completed their Visit 2 dosing, without safety findings that would meet the study's stopping or treatment discontinuation criteria (see Section 9). Subjects in the main treatment group in each cohort will also receive treatment in a staggered way, with 2 subjects starting first to receive doses and the remaining subjects starting to receive doses no sooner than approximately 22 h after the first two subjects of the main group have completed their Visit 2 dosing.

Visit 2 of cohort 4 will not be initiated until Visit 2 of cohort 3 has been completed.

All subjects will be given at the end of Visit 2, before discharge from the site, an adrenaline autoinjector and written instructions with an action plan on what to do if they develop a delayed allergic reaction (see Appendix 2).

Subjects will be contacted by telephone approximately 12 and 24 h after completion of dosing for a safety interview after each dosing visit.

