### **Visits 3, 4, 5 and 6**

After Visit 2, all subjects will return to the hospital on a biweekly basis for the subsequent dosings, to receive either a single s.c. injection or a series of 2 or 3 s.c. injections of the study medication. All dosings, except the 4th and 5th dosings of cohort 4, involve only single injections. In cohort 4, the administration of the study medication at Visits 5 and 6 involves 2 and 3 s.c. injections, respectively. There will be a minimum of 30 min interval between subsequent injections. Each injection will be given at a slightly different site of the exterior surface of the upper arm. The injections will alternate between the right and left arm.

On each of the Visits 3-6 dosing will be staggered in the same way as on Visit 2, ie. 2 sentinel subjects, 1 receiving DM-101 and 1 receiving placebo, will be dosed first in a double-blind fashion. Dosing of the remaining subjects in the cohort will be initiated no sooner than 22 h after the sentinel subjects have completed their dosing, without safety findings that would meet the study's stopping or treatment discontinuation criteria (see Section 9).

Subjects in the main treatment group in each cohort will also receive treatment in a staggered way, with 2 subjects starting first to receive doses and the remaining subjects starting to receive doses no sooner than approximately 22 h after the first two subjects of the main group have received their dosing.

Visit 5 dosing of cohort 4 will only take place after a favorable recommendation from the SRC, once it has reviewed all available safety data so far collected in the study, including data from Visit 5 of cohort 3.

Dosing will only be allowed if the study's stopping and treatment discontinuation criteria have not been met.

Subjects will be contacted by telephone approximately 12 and 24 h after completion of dosing for a safety interview after each dosing visit.

Table 12 (for cohort 3) and Table 13 (for cohort 4) (see Section 6.5) show the procedures that will take place, before and after dosing, during the visits. All subjects will remain confined in Turku University Hospital's Emergency Unit for approximately 6 h following their dosing, and may then be discharged if the medical review by the Investigator or a designee is satisfactory.

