### 9.1. Study Stopping Criteria

The Sponsor reserves the right to prematurely terminate the study for valid scientific or administrative reasons.

For reasons of safety, further dosing in the study will be suspended and all safety data will be reviewed by the SRC if any of the following happens:

- Death of a study participant possibly attributable to study treatment or procedure.
- One Grade 4 systemic allergic reaction according to the WAO classification, following injection of the study IMP.
- Two Grade 3 systemic allergic reactions according to the WAO classification, following injection of the study IMP in 2 participants in the same cohort.
- One Grade 4 injection site reaction in 3 participants in the same cohort.

If a decision to suspend dosing in the study is reached, the SRC will review thoroughly all safety data and will determine whether:

- Dosing (scheduled or adjusted) may be re-started in current or subsequent cohorts.
- The study must be stopped and no additional subjects be dosed.

The EC and the CA will be informed, if the study is terminated prematurely. The Investigator will proceed to appropriate actions concerning the study subjects in the case of premature termination of the study.

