## 9.2. Treatment Stopping Criteria

For an individual subject, dosing of study IMP will be discontinued if any of the following happens:

- One Grade 4 systemic allergic reaction according to the WAO classification, following injection of the study IMP.
- Two or more Grade 3 systemic allergic reactions according to the WAO classification, following injection of the study IMP.
- One Grade 4 injection site reaction.
- Two Grade 3 injection site reactions following two injections.
- An AE or need for medication not consistent with the protocol requirements that, in the judgment of the Investigator, presents an unacceptable consequence or risk to the subject.
- Inability or unwillingness to comply with the study protocol or protocol deviation that is considered sufficient to jeopardize the subject's well-being or the integrity of the study.
- Pregnancy during study participation.
- Withdrawal of consent

Discontinuation of dosing will not necessarily result in withdrawal of the subject from the study. For the subjects who discontinue treatment, all safety assessments scheduled for the Follow-up will be requested and observations will be recorded.

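### The second stagger step in cohorts 3 and 4 carries a 22 h wait but not the sentinel step's safety condition, so an event meeting only Section 9.2 in the first main pair does not expressly hold the last four subjects

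*Protocol*

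**What the plan says.** Each of cohorts 3 and 4 has 8 subjects, 6 on DM-101 and 2 on placebo (Protocol Section 3.2, Cohorts 3 and 4). Dosing at every visit runs in three groups: a sentinel pair (one active, one placebo), then two main-group subjects, then the remaining four.

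- **Sentinels to main group.** Two conditions apply: at least 22 h, and no safety finding that meets the stopping or treatment discontinuation criteria of Section 9.
- **First main pair to last four.** Only the time is stated. Section 3.2, Visit 2 has "the remaining subjects starting to receive doses no sooner than approximately 22 h after the first two subjects of the main group" have been dosed. Section 6.3, Visit 2 has "no sooner than approximately 22 h after the first two subjects of the main group have completed their Visit 2 dosing". For Visits 3-6, Section 3.2 has "no sooner than approximately 22 h after the first two subjects of the main group have received their dosing", and Section 6.3 matches it.

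Two general sentences apply to Visits 3-6. In Section 3.2, "dosing in each cohort will be allowed only if the study's stopping and treatment discontinuation criteria have not been met on the previous dosing visit". In Section 6.3, "Dosing will only be allowed if the study's stopping and treatment discontinuation criteria have not been met".

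Section 9.1 lists events that suspend dosing in the whole study. Its only injection-site rule is "One Grade 4 injection site reaction in 3 participants in the same cohort". Section 9.2 acts on one person: "For an individual subject, dosing of study IMP will be discontinued if any of the following happens".

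**The concern.** The same event is treated differently depending on who has it. If a sentinel meets a Section 9.2 criterion, the other six subjects wait. If one of the next two subjects meets it, that subject stops, and nothing in the stagger rule says the last four must wait. Section 1.4 presents the stagger as a way to limit exposure until early safety data are in, but a wait alone does not say that those data must be acceptable.

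An individual discontinuation criterion has already been reached in this trial without a study stop. The footnote to Table 7 gives as reasons for one active cohort 2 subject's discontinuation "withdrawal of consent and 2 Grade 3 local injection site reactions after 2 injections of IMP", while Section 1.2.3 reports that no study stopping criterion was met. That was under the version 1.1 rush regimen at higher doses. It shows that the situation can arise, not how often it would arise at 30 ng.

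What is at stake is 3 or 4 further active subjects being dosed after a finding that would have held the cohort one step earlier.

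**Working it through.** **1. Which events fall in the gap at Visit 2 (first dose in the cohort, one injection each, sentinels clear)**

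| Event | In a sentinel | In the first main pair |
|---|---|---|
| Death possibly attributable to study treatment or procedure; one Grade 4 systemic reaction; Grade 3 systemic reactions in 2 participants | Dosing suspended (9.1) | Dosing suspended (9.1) |
| Grade 4 injection site reaction in 1 or 2 subjects | Cohort held | Affected subjects stopped (9.2); no stated hold |
| AE the Investigator judges an unacceptable risk to the subject | Cohort held | Affected subject stopped (9.2); no stated hold |
| One Grade 3 systemic reaction | Neither 9.1 nor 9.2; dose adjustment only (9.3) | Same |

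The injection-site rule in 9.1 needs 3 participants. With clear sentinels, at most 2 can have the reaction at this point, so that rule cannot act before the last four are dosed. From Visit 3, the 9.2 criterion of two Grade 3 injection site reactions after two injections also comes within reach.

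**2. How many steps**

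- Visit 2: 1 × 2 cohorts = 2, with no condition beyond the wait.
- Visits 3-6: 4 × 2 cohorts = 8, ambiguous. The Section 6.3 sentence could be read as a same-visit hold, but it does not say whether it applies per subject or per cohort. Its counterpart in Section 3.2 refers to the previous visit.

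**3. How many active subjects**

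The plan's own split reproduces: 8 × 3/4 = 6 active and 8 × 1/4 = 2 placebo. After a sentinel pair of one active and one placebo, the main group is 5 active + 1 placebo. Assuming random order within it:

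- P(both of the first pair active) = C(5,2)/C(6,2) = 10/15 = 0.667; P(one active) = 5/15 = 0.333.
- Mean active in the pair = 2 × 5/6 = 1.67, against 1 in the sentinel pair.
- Last four: 3 active (0.667) or 4 active (0.333); mean 3 × 0.667 + 4 × 0.333 = 3.33.
- Over the two Visit 2 steps: 6 to 8 active, mean 6.67.

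**4. How likely the pair is to show such an event**

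The documents give no rate. Let p be an assumed risk per active subject at one visit, with none on placebo.

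P(at least one in the pair) = 0.667 × [1 − (1 − p)²] + 0.333 × p

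Multiplying by (1 − p) adds the condition that the sentinels are clear.

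| Assumed p | Sentinel pair shows an event | First main pair shows an event | Main pair shows an event and sentinels are clear |
|---|---|---|---|
| 1% | 1% | 1.7% | 1.6% |
| 5% | 5% | 8.2% | 7.8% |
| 10% | 10% | 16% | 14.4% |

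The main pair is about 1.6 times as likely as the sentinel pair to reveal the event.

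**5. What earlier exposure can say**

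In cohort 1, 0 of 4 active subjects had a severe TEAE at 30 ng (Table 6). The one-sided 95% upper limit is 1 − 0.05^(1/4) = 0.527, or 53%. A severe TEAE is not the same outcome as a 9.2-only event, so this does not bound p. It shows only how little four subjects can exclude.

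**The case against.** The strongest reply is that other text and ordinary judgement close most of the gap.

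- **Section 1.2.3** makes repeated dosing and escalation within these cohorts depend on safety and on the Section 9 discontinuation or adjustment criteria, with no limit to the previous visit. This helps at Visits 3-6, but it does not say whether one subject's event holds the others at the same visit. It does not reach the first 30 ng dose at Visit 2.
- **Section 3.3** lets Section 9 observations trigger extra committee meetings, and the committee's detailed procedures are in a separate document not available here. In cohort 2 the committee did recommend ending further dosing although no stopping criterion was met. That is a working route, but it is discretionary. The committee met at the Principal Investigator's request, after dosing had already been halted.
- **Section 5.1.6.2** asks the Investigator to discuss findings of concern with the Medical Monitor before dosing. This belongs to the pre-dose review and is not a stated hold.
- **The Visit 2 trigger is remote.** Grade 4 in Table 14 means necrosis, exfoliative dermatitis, or an emergency visit or hospitalisation, here after one 30 ng injection. The other trigger is already a matter of Investigator judgement. The cohort 2 example needed two injections and could not occur at Visit 2. This stands, and it is why the point is minor.
- **The rates are assumed.** This also stands. They show scale only.
- **The asymmetry may be deliberate**, with the stricter hold kept for the least-informed pair. The protocol gives no such reason, and the first main pair is expected to contain more active subjects than the sentinel pair.

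**Conclusion.** The point holds, at low severity. At Visit 2 of both cohorts the written rule releases the last four on time alone, and neither 9.1 nor 9.2 supplies a hold for a Grade 4 injection site reaction in the first main pair. At Visits 3-6 the text can be read either way. Followed as written, the rule could dose 3 or 4 more active subjects per step after a finding that would have held the cohort in a sentinel. The head counts rest on the 6:2 split, a sentinel pair of one active and one placebo, and random order in the main group. The probabilities rest on assumed rates. Discretion by the Investigator, Medical Monitor and committee makes the practical risk smaller than the text alone implies.

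**What to change.** In the main-group stagger sentence of Sections 3.2 and 6.3, for both Visit 2 and Visits 3-6 (four places), repeat after the 22 h wait the safety condition that already ends the sentinel sentence, with its reference to Section 9. A finding in the first main pair that meets a stopping or treatment discontinuation criterion would then hold the remaining four. Add a few words on who reviews the finding and releases dosing, since the existing clause does not say. The change would not act on a single Grade 3 systemic reaction, which falls only under 9.3.

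The cost is one amendment. Because the change bears on subject safety, Section 11.4 points to a substantial amendment with ethics committee and authority approval. No new visits, staff or assessments are needed: the 6 h confinement and the 12 h call already fall within the 22 h wait. The downside is a possible dosing delay when such an event occurs.

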### **VISITS 3-6**

After Visit 2, dosing in each cohort will be allowed only if the study's stopping and treatment discontinuation criteria have not been met on the previous dosing visit (see Section 9).

All subjects will return to the hospital for another 4 visits (Visit 3, Visit 4, Visit 5 and Visit 6) on a biweekly basis for the subsequent dosings. In cohort 3, subjects will receive a single s.c. injection on each of these visits. In cohort 4, subjects will receive a single s.c. injection on Visits 3 and 4 and a series of 2 or 3 s.c. injections on Visits 5 and 6, respectively, with a minimum of 30 min interval between subsequent injections. Each injection will be given at a slightly different site of the exterior surface of the upper arm. The injections will alternate between the right and left arm.

Dose escalation to the 200 ng daily dose (Visit 5) in cohort 4 will only take place after a favourable recommendation from the SRC, once it has reviewed all available safety data so far collected in the study, including data from Visit 5 of cohort 3.

On each of the Visits 3-6, dosing will be staggered in the same way as on Visit 2, i.e. 2 sentinel subjects, 1 receiving DM-101 and 1 receiving placebo, will be dosed first in a double-blind fashion. Dosing of the remaining subjects in the cohort will be initiated no sooner than 22 h after the sentinel subjects have completed their dosing, without safety findings that would meet the study's stopping or treatment discontinuation criteria (see Section 9). Subjects in the main treatment group in each cohort will also receive treatment in a staggered way, with 2 subjects starting first to receive doses and the remaining subjects starting to receive doses no sooner than approximately 22 h after the first two subjects of the main group have received their dosing.

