Treatment on Day 1 was to start with administration of 100 ng of DM-101 or placebo. This was to be followed by administration of progressively escalating doses of DM-101 or placebo, at approximately 30 min intervals, up to a total of 6 s.c. injections per subject/day. On Day 2, treatment was to start with a repeat of the top DM-101 dose administered on Day 1 or placebo, followed by another 2 administrations of escalating DM-101 doses or placebo, approximately 30 min apart, up to a maximum of 3 s.c. injections per subject/day. Dose escalation, in each subject, was to be allowed only if the study's stopping and treatment discontinuation-adjustment criteria were not met (see Section 9).

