#### **3.3. Safety Review Committee**

For this study, a SRC has been assembled. After completion of cohort 1 and cohort 2 and the interim data analysis, the SRC is responsible for 1) providing recommendations on the dose escalation from 100 ng to 200 ng in cohort 4 based on the safety data collected up to and including cohort 3 Visit 5 and cohort 4 Visit 4, i.e. prior to cohort 4 Visit 5, where the administration of 200 ng dose is planned; 2) on continuation of dosing of cohort 3 to Visit 6; 3) on continuation or termination of the study; 4) on possible suspension or modification of dosing based on the study's stopping criteria (see Section 9); 5) on the appropriateness of the safety measures and the possible need for alterations. If needed, the study will be halted until appropriate measures have been taken to amend the study protocol and until all relevant approvals have been received to continue the study.

Additional SRC meetings will be held, as needed; additional meetings will be triggered by safety observations as described in Section 9.

The SRC includes members with experience in the conduct and risk assessment/management of clinical trials and ethical aspects. The SRC is comprised of the Principal Investigator, the Sponsor's Medical Monitor, representative(s) of the Sponsor and a qualified biostatistician.

Detailed instructions for SRC meetings and its decision-making process are described in a separate document called "SRC Instructions". The study data will be reviewed blinded. However, if it is deemed necessary for ascertaining the safety of the study subjects, the review may also be unblinded.

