## 9.3. Dose Adjustment Criteria

For each individual subject, dose escalation will be halted and dosing will be adjusted according to the following:

- If a Grade 3 systemic allergic reaction, according to the WAO classification, or a Grade 3 injection site reaction occurs, following administration of a dose of the study IMP, the previous well-tolerated daily dose level should be repeated at the time the next dosing is scheduled. If this is found to be tolerated, the subject will continue to receive the same, tolerated dose level at each subsequent scheduled dosing. Further dose escalation according to the protocol's pre-defined scheme should not be attempted. The number of doses scheduled for one dosing day should not be exceeded.

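### Cohort 4: after one Grade 3 reaction at Visit 5, the sentinel step before 300 ng can be passed at 100 ng, because the release rule requires neither the planned dose nor the absence of a dose-adjustment finding

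*Protocol*

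**What the plan says.** **Doses.** Protocol Table 8 gives cohort 4 daily doses of 30, 50, 100, 200 and 300 ng at Visits 2 to 6. Cohort 3 stops at 100 ng.

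**Release rule.** At each visit one DM-101 and one placebo sentinel go first. Section 6.3 states: "Dosing of the remaining subjects in the cohort will be initiated no sooner than 22 h after the sentinel subjects have completed their dosing". Section 3.2 attaches the condition: "after the sentinel subjects have completed their dosing, without safety findings that would meet the study's stopping or treatment discontinuation criteria (see Section 9"). Section 6.3 adds a general sentence: "Dosing will only be allowed if the study's stopping and treatment discontinuation criteria have not been met". None of these mentions the sentinel's dose level or the adjustment criteria.

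**Thresholds.** For Grade 3 reactions, Section 9.1 suspends the study on "Two Grade 3 systemic allergic reactions according to the WAO classification, following injection of the study IMP in 2 participants in the same cohort". It has no Grade 3 rule for injection site reactions; those count only at Grade 4, in three participants. Section 9.2 stops an individual after two or more Grade 3 systemic reactions, or on "Two Grade 3 injection site reactions following two injections". A single Grade 3 reaction of either kind falls to Section 9.3. That section applies subject by subject and returns the subject to the previous tolerated level. If that level is tolerated, "the subject will continue to receive the same, tolerated dose level at each subsequent scheduled dosing".

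**Committee.** Section 3.3 charges the SRC with "providing recommendations on the dose escalation from 100 ng to 200 ng in cohort 4", on data that include cohort 4 Visit 4. It schedules no review between 200 and 300 ng.

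**Other wording.** Sections 1.2.3 and 12 say that escalation within cohorts also depends on the adjustment criteria. The cohort 2 text in Section 3.2 made this explicitly individual: "Dose escalation, in each subject, was to be allowed only if the study's stopping and treatment discontinuation-adjustment criteria were not met".

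**The concern.** A sentinel step protects the rest of the cohort only if the sentinel has taken the dose that the others are about to take. Here the step can be satisfied by a sentinel who has been moved to a lower dose because of a reaction.

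No earlier cohort has tested 200 or 300 ng in this regimen. At Visit 6 no committee review is scheduled either, so the sentinel step is the main required cohort-level check before 300 ng. At stake is whether the five DM-101 subjects of the main group reach 300 ng after a real test of that dose, or after a step that is complete on paper only.

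**Working it through.** **Inputs.** Dose ladder: Table 8. Criteria: Sections 9.1 to 9.3. Allocation of 6 DM-101 and 2 placebo per cohort: Section 3.2. Maximum of 100 ng per injection: Section 1.4. One sentence in Section 1.2.3 places 200 and 300 ng one visit earlier; I follow Table 8 and Sections 3.2 and 6.3.

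**1. The plan's own total.** 30 + 50 + 100 + 200 + 300 = 680 ng, as Table 8 states.

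**2. Apply 9.3 to the active sentinel.** With a first Grade 3 reaction at Visit 5 (200 ng), the sentinel's doses at Visits 2 to 6 become 30, 50, 100, 200 and 100 ng. The Visit 6 step is run at 100 ng and the main group is due 300 ng.

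**3. Does anything required block release?** One Grade 3 reaction meets no reaction threshold in 9.1 or 9.2, so the release condition and the general sentence in 6.3 are both satisfied. The same holds at the full dose: a single Grade 3 reaction in the sentinel at 200 ng (Visit 5) or 300 ng (Visit 6) does not block release at that visit.

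**4. Earlier reactions.** A first Grade 3 reaction at Visit 3 or 4 holds the sentinel at 30 or 50 ng. Both precede the SRC review required before 200 ng, so the committee would see them. Only the Visit 5 event has no scheduled review after it.

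**5. A second event.** Suppose the sentinel has had one Grade 3 reaction and one subject in the first main-group pair then has one:

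| Sentinel | First main pair | 9.1 met? |
|---|---|---|
| Systemic | Systemic | Yes: dosing suspended |
| Systemic | Injection site | No |
| Injection site | Systemic | No |
| Injection site | Injection site | No |

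Section 9.1 sets no same-visit limit, so the first row already stops the remaining four subjects.

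**6. Size.**
- Daily total at Visit 6: 300/100 = 3-fold.
- Single injection: 100/100 = 1-fold.
- A main-group subject's own step: 300/200 = 1.5-fold.
- Main group: 6 − 1 = 5 DM-101 and 2 − 1 = 1 placebo.
- First pair in random order: two DM-101 with probability C(5,2)/C(6,2) = 10/15 = 67%; one with probability 5/15 = 33%; never none. The mean is 2 × 5/6 = 1.67.

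In the last three rows of the table, all 5 DM-101 subjects can receive 300 ng with no cohort-level check against 9.3. With the fix, 1 or 2 would do so before such a check. This contrast does not apply to the first row.

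**7. Frequency.** The documents give no Grade 3 rate at 30 to 200 ng. Purely as an assumption, let the risk be an equal p at each of Visits 3, 4 and 5. The chance that the active sentinel's first Grade 3 reaction falls at Visit 5 is (1 − p)² × p, which is 4.5%, 8.1% and 12.8% for p = 0.05, 0.10 and 0.20. This shows scale and is not an estimate.

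**The case against.** **The tiers look deliberate.** One Grade 3 event adjusts the individual; Grade 3 systemic events in two participants suspend dosing. That suits immunotherapy, where each subject escalates to a tolerated or target dose. Section 9.3 still protects every main-group subject individually: anyone with a Grade 3 reaction of their own is held. This stands. What is missing is a check at cohort level.

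**Sections 1.2.3 and 12 may already close the gap.** Read at cohort level, they would block escalation after a 9.3 finding. That reading is possible. The cohort 2 phrase about each subject was not carried over, so it cannot prove that the later text is individual. But Section 9.3 is itself written per subject and lets dosing continue, and the operative rules in 3.2 and 6.3 omit it. The text is ambiguous at the point where staff must apply it.

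**Discretion exists.** The investigator may stop a subject on judgement (9.2), should discuss findings of concern with the Medical Monitor before dosing (5.1.6.2), and the SRC can meet as needed (3.3). The SRC's own instructions are not among the documents and may contain more. None of the routes shown is a required hold. Grade 2 to 5 systemic reactions must reach the sponsor within 24 h (8.4.1), which can be later than a 22 h release. Section 8.4.2 sets no such deadline for injection site reactions.

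**A reader might infer more.** One might conclude that the main group can reach 300 ng behind a sentinel held at 30 or 50 ng without anyone looking, or that nothing would stop the cohort after repeated reactions. The documents do not support either: the SRC review before 200 ng covers the first, and 9.1 covers a second participant's Grade 3 systemic reaction.

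**Conclusion.** The concern holds in a limited form: a cheap improvement, with medium confidence. The release rule does not tie the sentinel step to the visit's dose and leaves out criteria that the protocol elsewhere makes a condition of escalation.

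The remaining gap is the first Grade 3 event in a sentinel, at Visit 5 or at the full 200 or 300 ng, and sequences that involve a Grade 3 injection site reaction. Its extent is bounded by the 100 ng limit per injection and the 1.5-fold individual step.

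The Visit 6 path assumes that the same sentinels go first at every visit. The cohort 2 text said so; the text for cohorts 3 and 4 does not name them, and does not require a held sentinel to be replaced. The full-dose path needs no such assumption. The subject counts assume that all eight subjects remain and that no main-group subject has been held.

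**What to change.** In Sections 3.2 and 6.3, with a matching line in 3.3:

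- The sentinel step counts only if both sentinels receive the visit's full planned level (active or matching placebo) with no finding that meets 9.1, 9.2 or 9.3.
- If a sentinel has been held or stopped, the first main-group pair still on the full schedule serves as the sentinel step, under the same criterion and the existing 22 h gap.
- If a sentinel step shows a 9.3 finding, or a sentinel was held at Visit 5, a blinded ad hoc SRC review decides whether the remaining subjects proceed to that level. Do not impose an automatic repeat of the previous level: Visit 6 is the last dosing visit, so that would rule out 300 ng without a decision.

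No unblinding or extra staff is needed. With one placebo subject in the main group, any pair includes at least one DM-101 subject, and volumes are identical for active and placebo at each level. If the substitute pair passes, the minimum stagger stays at 22 + 22 = 44 h, apart from any SRC review.

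**Cost.** A possible delay or one extra SRC review, including when the held sentinel is on placebo. After a Visit 5 hold the review fits in the 14 days before Visit 6. After a finding at the visit itself it must fit the ±2 day window. If the SRC declines escalation, some subjects miss 300 ng for reasons other than their own tolerance. Report them separately in the secondary endpoint on reaching the pre-defined dose (Protocol 2.2.2 and 10.10; SAP Section 14).
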